SDR 21-141: Developing and Testing a COVID-19 Vaccination Acceptance Intervention

Multiple PIs: [name] MPH (corresponding), [name], [name]

[Version Number 5.0 Version Date 12.15.23]

Abstract

Background: The COVID-19 pandemic has resulted in significant loss of life with total case and death counts increasing daily. COVID-19 vaccines are effective in preventing symptomatic disease, severe disease, disease transmission, and death. Despite the efficacy and safety of COVID-19 vaccines, many people remain hesitant about vaccination with increased hesitancy among younger individuals (less than 50 years old), Black and Hispanic adults, and those living in rural areas. Recent surveys of Veterans indicate that approximately 35% are unsure whether they will receive a vaccine, highlighting the critical need for evidence-based motivational interventions to increase COVID-19 vaccine acceptance in this population who, without vaccination, remain at risk of severe adverse outcomes and death. The overall objective of this study is to implement and test a COVID-19 vaccine acceptance intervention that is responsive to the needs of Veterans and VA healthcare providers (HCPs) and staff. VA HCPs and PACT staff are consistently identified by patients as trusted sources of vaccine information, thereby best suited to initiate vaccine acceptance discussions with patients. Methods: This evidenceinformed Vaccine Acceptance Intervention will be conducted in VISNs 16 and 21 as a Hybrid Type 2 pragmatic implementation-effectiveness trial, guided by the i-PARiHS framework, and using Implementation Facilitation as the overarching implementation strategy. The specific aims are as follows: Aim 1) Examine the effectiveness of a Vaccine Acceptance Intervention versus Usual Care on Veterans' vaccination rates in a one-year cluster randomized controlled trial. The implementation team will include VISN-level external facilitators, VAMC- level internal facilitators, and clinic-level site champions to support PACT staff and Whole Health Coaches and Peers in implementing the Vaccine Acceptance Intervention with Veterans. Aim 2) Survey Veterans to understand what factors are associated with the decision to accept or not accept COVID vaccination among previously unvaccinated Veterans and through gualitative interviews, learn more about these factors and how they differ between sociodemographically and clinically diverse Veteran subgroups. Aim 3) Learn what aspects of the Vaccine Acceptance Intervention and implementation strategies were helpful and not helpful in improving Veteran vaccine acceptance by conducting mid-trial and end-of-trial gualitative interviews with VISN 16 and 21 study stakeholders using purposive sampling of VA staff and HCPs from sites with high and low vaccination rates. Impact: This is the first multi-site randomized controlled trial to test an MIinformed vaccine acceptance intervention that can be rapidly scaled across VA to improve COVID-19 vaccine acceptance in Veterans. Furthermore, information gained will be used to inform healthcare systems' strategies to improve future vaccination and public health campaigns.

List of Abbreviations

ACTIV-3 Accelerating COVID-19 Therapeutic Interventions and Vaccines AE- Adverse Event CAN Scores- Care Assessment Need Scores CAVHS- Central Arkansas Veterans Healthcare System CDC- Centers for Disease Control and Prevention **CDW- Clinical Data Warehouse** CEAL- Community Engagement Alliance Co-I- Co-Investigator COVID-19- Coronavirus disease 2019 **CRE- CREATE** CSHIIP- Center for the Study of Healthcare Innovation, Implementation & Policy DART- Data Access Request Tracker **DoD-** Department of Defense FDA- Food and Drug Administration GLVA- Greater Los Angeles Veteran Affairs HBC- Health Behavior Coordinator **HCP- Health Care Provider** HIPAA- Health Insurance Portability Accountability Act HPDP- Health Promotion Disease Prevention **IF-** Implementation Facilitator **ICN- Integration Control Number IIR-** Investigator Initiated Research i-PARiHS- integrated Promoting Action on Research Implementation in Health Services IRB- Institutional Review Board **MD-** Doctor of Medicine MHS- Mental Health Specialty MI- Motivational Interviewing MIRECC- Mental Illness Research Education and Clinical Center MWCCS- Multicenter AIDS Cohort Study and the Women's Interagency HIV Study NCP- National Center for Health Promotion and Disease Prevention NIH- National Institutes of Health OARS- Open Questions, Affirmations, Reflections, Summaries OHE- Office of Health Equity **OI&T-** Office of Information and Technology PACT- Program Aligned Care Team PCORI- Patient Centered Office and Research Institute PEI- National Partnered Evaluation Initiative PHD- Doctor of Philosophy PHI- Protected Health Information PI-Principal Investigator POC-Point of Contact PTSD- Post-Traumatic Stress Disorder **OUERI-** Ouality Enhancement Research Initiative **RRT-** Rapid Response Team SAE- Serious Adverse Event SARS CoV-2- Severe Acute Respiratory Syndrome Coronavirus-2 SCALE- Veteran and Staff Perceptions of VHA Large Scale Adverse Event Communications SFVAHCS- San Francisco Veteran Affairs Health Care System

SQL- Structured Query Language

2.0 Introduction

COVID-19 is now the leading cause of death in the U.S. As of August 2021, there were over 35 million cases and over 600,000 deaths attributed to COVID-19 in the U.S. COVID-19 has had a devastating impact on society, with racial and ethnic minority populations most adversely affected by the pandemic.¹ In December 2020, the FDA granted emergency use authorizations for the first COVID-19 vaccines. As of August 2021, 68% of the U.S. population ages 12 and older had received at least one dose of the vaccine and 58% are fully vaccinated.² Veteran vaccination rates are lower, with recent reports citing that 47% of Veterans have received at least one dose. The emergence of vaccines has reduced COVID-19 cases and deaths, but overall acceptance of the vaccine is declining. This leaves those who remain unvaccinated at risk of severe disease and death.

Reasons for vaccine hesitancy are multi-factorial. The World Health Organization defines vaccine hesitancy as "a delay in acceptance or refusal of vaccination despite availability of vaccination services."³ Vaccine hesitancy is complex and context specific, varying across time, place, and vaccines. It is influenced by factors such as complacency, convenience and confidence. Reasons for not getting vaccinated include barriers such as lack of transportation or access to psychological services and cognitive barriers including perceived lack of risk, need for vaccine, or social benefit, which may be more pronounced in individuals with lower levels of education,⁴ and underlying mental health and substance use disorders.^{5,6} Additional barriers include negative attitudes toward vaccines, prior negative experiences with vaccination (i.e., needle phobia), misinformation about vaccines (e.g., belief that the vaccine causes COVID), and general lack of trust in the healthcare system and government.⁷ In a recent study, the most cited reasons for COVID-19 vaccine hesitancy included (1) concerns about side effects, safety, and efficacy, and (2) the unprecedented speed with which the vaccine was developed, manufactured and approved for emergency use authorization.⁸

Sociodemographic factors are associated with greater COVID-19 vaccine hesitancy or distrust, including younger age (< 50 years old), Black or Hispanic ethnicity, lower education, rurality, Republican or independent political partisanship, and not having received a flu vaccine in the prior year.^{8,9} Vaccination rates are higher in White adults (50%) compared to Black and Hispanic adults (36%). Similarly, 16% of White adults say they will "Wait and see" before deciding to receive a vaccine compared to 24% of Black and Hispanic adults.¹ The above sociodemographic data are from non-VA sources. Current Veteran vaccination rates are lower overall and vaccination rates are higher in Black Veterans compared to White and Hispanic Veterans (details on vaccination rate data for VISN 16 and 21 Veterans are in the Appendix).

Low vaccination rates among Black and Hispanic/Latinx populations may be attributed to greater distrust of COVID-19 vaccine safety and scientists and medical providers compared to Whites. In "Distrust, Race and Research," a landmark 2002 JAMA Internal Medicine study, Corbie-Smith and colleagues found that compared with White Americans, Black Americans were more likely to believe that physicians would ask them to participate in harmful research, expose them to unnecessary risks, not fully explain the research, or treat them as part of an experiment without their consent.¹⁰ This mistrust among racial/ethnic minorities must be considered within the larger context of systemic racism as well as historical trauma associated with research and healthcare in the U.S.^{11,120}

COVID-19 vaccination rates may vary widely by geographic regions. As of early August 2021, 46% of Veterans in VISN 16 and 58% of Veterans in VISN 21 have received at least one dose of the vaccine. Variation in vaccination rates are even more pronounced at the Veterans Administration Medical Center (VAMC) facility level. In VISN 16, 63% of Veterans in New Orleans, LA have received at least one dose compared to 39% of Veterans in Alexandria, LA. These findings are consistent with overall vaccine acceptance trends which have demonstrated higher vaccination rates in urban centers compared to rural areas.^{13,14} Lower COVID-19 vaccination rates in rural communities is concerning given that compared with their urban

counterparts, rural adults are at higher risk for the chronic diseases (i.e., heart disease, COPD, diabetes, obesity, cancer)¹⁵ that are also associated with worse COVID-19 clinical outcomes.¹⁶ In rural communities, racial and ethnic disparities in access to care and health outcomes persist,¹⁷ which may lower vaccination rates further.

Healthcare providers' (HCP) recommendations about vaccination is strongly associated with patients' acceptance of vaccination.¹⁸ In VA, HCPs include all members of the Patient Aligned Care Teams (PACT), i.e., the medical providers (physicians and nurse practitioners), registered nurse (RN) care managers, licensed vocational nurses, medical support assistants, social workers, dieticians, pharmacists, and mental health providers embedded in primary care. HCPs are more likely to recommend vaccination to patients if they were vaccinated themselves, hold positive attitudes about vaccination, are knowledgeable about vaccination (e.g., understand and can articulate efficacy, safety and value), and are confident in leading vaccination conversations with patients. Thus, *provider trainings in communication* strategies may be an important strategy in increasing vaccine uptake in patients, especially as vaccination rates have been declining in recent months.¹⁹

Scientists speculate that COVID-19 may become an endemic virus²⁰ and boosters may be required to protect individuals from variants and declines in immunity over time. Current studies show that two doses of the mRNA vaccines- those produced by Pfizer and Moderna-confer more than 90% efficacy and that immunity lasts at least six months after **completing vaccination**.^{21,22} The Johnson and Johnson single-dose vaccine has similar effectiveness and durability.²³ Nevertheless, all three companies are currently testing COVID-19 boosters. This is because researchers suspect that immunity might wane over time, such as after one year or more, and might not provide sufficient protection against coronavirus variants that could emerge and evolve. Therefore, a vaccinated person might need a booster dose to stay protected against the original coronavirus strain, as well as newly emerging variants, similar to the rationale for administering the seasonal flu vaccine annually. Currently, the need for and timing for COVID-19 booster doses has not been established, and at this time, booster doses of

COVID-19 vaccine are not recommended by the CDC (Interim Clinical Considerations for Use of COVID-19 Vaccines | CDC). Nevertheless, in late May 2021, the U.S. Surgeon General [name] has told Americans to be prepared to have a COVID-19 vaccine booster within one year.²⁴ One question currently under investigation is whether the booster vaccine will be the same or a different product from the original COVID-19 vaccine.²⁵ Thus, if and when booster doses of COVID-19 vaccine are approved and recommended for Americans, the VA may find itself in a similar position of needing strategies to overcome similar or even greater barriers to booster dose acceptance than with the original COVID-19 vaccines. This study will use surveys and qualitative interviewing techniques to explore Veterans' and VA staff attitudes and perceptions of COVID-19 booster vaccination.

More immediately, the CDC has released updated guidance that the flu vaccine may be given at the same time as the COVID-19 vaccination, provided the individual is not ill at the time.²⁶ This updated guidance is because there have been no reports of reduced immunogenicity with the administration of both vaccines simultaneously, as originally thought. It is recommended that each vaccine be given at different anatomical sites (different limbs) as an intra-muscular injection to mitigate local reaction. Given concerns about co-infection with seasonal flu and COVID-19, for Veterans not yet vaccinated against COVID-19, but who regularly get flu vaccine, messaging and coaching could be targeted to encourage uptake of both vaccines and simultaneous administration for convenience.

Preliminary Studies in addition to ongoing Phase I Pre-implementation Project

1. Telephone Motivational Coaching to Encourage Flu Vaccination and Prevent COVID-19 Co-Infection in High-Risk Patients within the SFVAHCS: A Quality Improvement Study (10/16/20-12/7/20) ([name] and [name], mPIs).

Objective: To conduct a Quality Improvement (QI) study to examine the feasibility of motivational interviewing (MI)-informed outreach calls for seasonal flu vaccination acceptance among higher-risk unvaccinated Veterans in the SFVAHCS.

Methods: First, Whole Health coaches and other staff members trained in Whole Health and motivational interviewing (MI) participated in a brief training focused on using MI to encourage acceptance of the seasonal flu vaccine. The VA National Center for Health Promotion and Disease Prevention (NCP), "Moving to Vaccine Acceptance" scripts were adapted as electronic medical record (EMR) note templates that served as scripts, and upon completion, as documentation of the telephone encounter. VA administrative data were used to identify 198 Veterans in the SFVAHCS with Care Assessment Need (CAN) scores > 95 with no documentation of having received seasonal flu vaccine. After patients confirmed not having received the seasonal flu vaccine, a Whole Health coach, Peer Specialist, or other VA staff member engaged them in an MI-styled telephone conversation about their interest in and barriers to receiving flu vaccine, especially in light of risk for co-infection with COVID-19 and flu. Consistent with MI communication, coaches asked opened-ended questions, listened in a non-judgmental manner, and asked permission to share information about flu vaccine, including specific information about where and when they could receive flu vaccination.

Results: 488 Veterans were initially identified for the intervention. VA staff made MI-styled flu outreach calls from 10/16/20 through 12/7/20. Of the original 488 Veterans, 290 veterans reported having already received a flu vaccine (although not documented), resulting in 198 veterans remaining eligible for the intervention (see **Table 1** below). The mean age was 73.4 years (SD±11.2 years), 96% were male, 56% were rural, 70% were Caucasian, and 4% were Hispanic. Overall, 53 patients (27%) received vaccinations within 30 days of an MI coaching call. Vaccination rates within 30 days were highest among Veterans 85 and older (47%) followed by Veterans 75-84 (27%). Unexpectedly, rates were higher among Veterans who received primary care at rural versus urban facilities (40% vs. 21%) and who resided in rural areas (32% vs. 23%). Due to the small number of women and ethnic minority Veterans, we were unable to detect differences in these subgroups.

Discussion/Limitations: There were several limitations to this QI project including that the sample was small, single-site and a non-generalizable population of the oldest and sickest Veterans in the health care system. The rapid pace of the seasonal vaccination cycle underscored the importance of up-to-date and accurate vaccination information for prioritizing staff resources. The oldest and rural Veterans benefitted the most from the MI-styled flu outreach calls perhaps because they were the most isolated and lacked ready access to flu vaccine services.

Conclusion/Impacts: This QI project demonstrated the feasibility of MI-styled outreach calls to encourage flu vaccination, which might generalize to other vaccines such as COVID-19. It also demonstrated that a work force of VA Whole Health Coaches, Peer Specialists, and others trained in Whole Health can be quickly re-purposed to use their MI and coaching skills to promote a target health behavior, in this case, seasonal flu vaccination to decrease risk for COVID-19 co-infection.

| | Total | Not Vaccinated | | Vaccinated | | p |
|---------------------------------------|----------------|-------------------|------------------|------------|----------|------|
| | 198 | 145 | (73.2) | 53 | (26.8) | |
| Age | | | | | | |
| mean (sd) | 73.4 (11.2) | 72.2 | (11.3) | 76.9 | (10.2) | .009 |
| 18-54 years | 7 | 7 | (100.0) | | | |
| 55-64 years | 30 | 23 | (76.7) | 7 | (23.3) | |
| 65-74 years | 64 | 50 | (78.1) | 14 | (21.9) | |
| 75-84 years | 67 | 49 | (73.1) | 18 | (26.9) | |
| 85+ years | 30 | 16 | (53.3) | 14 | (46.7) | .048 |
| Sex | | | | | | |
| Male | 190 | 139 | (73.2) | 51 | (26.8) | |
| Female | 8 | 6 | (75.0) | 2 | (25.0) | .908 |
| Marital Status | | | | | | |
| Married | 62 | 43 | (69.4) | 19 | (30.6) | |
| Never Married | 38 | 26 | (68.4) | 12 | (31.6) | |
| Divorced, Separated, or Widowed | 96 | 74 | (77.1) | 22 | (22.9) | |
| Unknown | 2 | 2 | (100.0) | | | .497 |
| Rural Patient Residence | | | | | | |
| Urban | 111 | 86 | (77.5) | 25 | (22.5) | |
| Rural | 87 | 59 | (67.8) | 28 | (32.2) | .128 |
| Rural or Urban Clinic or Medical Cent | er | | 20 - 20 - 20 | | 28 820 B | |
| Urban Medical Center or Clinic | 135 | 107 | (79.3) | 28 | (20.7) | |
| Rural Clinic | 63 | 38 | (60.3) | 25 | (39.7) | .005 |
| Race and Ethnicity | | | | | | |
| White, Not Hispanic | 119 | 85 | (71.4) | 34 | (28.6) | |
| Racial or Ethnic Minority | 44 | 34 | (77.3) | 10 | (22.7) | |
| Unknown | 17 | 11 | (64.7) | 6 | (35.3) | .584 |
| Service Connected | | 0 | | | | |
| Not Service Connected | 97 | 75 | (77.3) | 22 | (22.7) | |
| Service Connected | 101 | 70 | (69.3) | 31 | (30.7) | .203 |

Table 1. 30-Day Influenza Immunization Rates for 198 Unvaccinated Veterans Contacted (10/16/2020 – 12/7/2020)

2a. Qualitative Interviews to Understand COVID-19 Vaccine Intentions in Veterans.

[name] (Co-I), co-lead of the Bridge QUERI Rapid Response Team, led a quality improvement project to inform the National Center for Health Promotion and Disease Prevention's vaccination efforts in VA. Semi-structured qualitative interviews (N=59) were conducted with Veterans (N=29) and VA staff members (N=30).

Qualitative interviews with Veterans indicated that "vaccine skepticism" was the most common form of vaccine hesitancy, But there's always a fear like what's in this injection, like is it a tracker? Lack of concern about COVID-19, or "vaccine indifference", was cited by some Veterans, No, I don't expect that I'll get it [COVID-19]. I think if I was gonna get it I would have had it by now." And other Veteran stated, "I mean, I take care of myself when it comes to eating good and you know, taking my vitamins and things like that. So, I try to keep as healthy as possible, so if I was to contract anything my body could fight it off as best I could." Distrust was another barrier to vaccine acceptance. One Veteran stated, "I saw it wasn't FDA approved and I see how fast they rush this stuff." Another Veteran expressed overall distrust of the system, "I know a lot of people who have never gotten the flu shot ever in their lives. If they did, it was because it was required of them. You know, we just don't trust this system. It's not that we don't trust science." Interviews highlighted the unique barriers to vaccine acceptance in the Veteran population. One Veteran stated, "...I've been, you know, in the military and I went in the Marine corps and I was exposed to a whole bunch of chemicals and now I'm sick from them and I don't want--I don't want any more like chemicals added to my body that don't have to be added to my body."

2b. Surveys of Veteran attitudes and intentions regarding COVID-19 vaccination. [name] and the Bridge OUERI Rapid Response Team collaborated with SHEP to survey Veterans (N=1,178) through SHEP's ongoing Veterans Insights Panel (VIP). The survey was fielded March 12-28, 2021. Of those surveyed, 29% (N=339) reported that they had not been vaccinated. Unvaccinated Veterans were asked about their intent to vaccinate and 13% reported that they would probably not receive the vaccine, 22% were unsure, and 13% said they would probably receive the vaccine. Additionally, 27% reported they would definitely not receive the vaccine and, in contrast, 25% stated they would definitely receive the vaccine. Veterans' self-report of their overall health varied by vaccination intention. Those who were "not sure" whether they would receive the vaccine were more likely to describe their overall health as fair/poor (43%) than those who would definitely/probably get vaccinated (30%), and 24% of those who said they would definitely/probably not get vaccinated reported fair/poor overall health. Similar trends were found regarding Veteran self-report of mental health status. Veterans who were "not sure" if they would get vaccinated were more likely to describe their mental health as fair/poor (44%) compared to those who expressed an intention to get vaccinated (37%), or remain unvaccinated (21%). Veterans cited a range of reasons for not getting vaccinated including concerns about vaccine side-effects, preference to use as few medicines as possible, vaccine distrust, healthcare system distrust, a preference to gain natural immunity (from contracting COVID-19), and a desire to wait to before making a decision about COVID-19 vaccination.

Thus, there is a sizable proportion of unvaccinated Veterans (~35%) who remain unsure or who *might* accept COVID-19 vaccination, sometimes referred to as the "moveable middle". Reasons for delaying or refusing vaccine largely relate to general distrust of medicine and healthcare, and specific skepticism and distrust of the vaccine. In addition, as the pandemic continues, there is apathy, indifference, and a decreased perception of risk. This trial targets this actionable group of Veterans in testing an intervention intended to spark communication with VA providers to move patients toward vaccine acceptance.

Risks of infection, severe disease, and death due to COVID-19 persist for the unvaccinated. While cases, hospitalizations and death to COVID-19 are overall declining, these numbers include the approximately 60% of adults who have received at least one vaccination.²⁷ When adjustments are made to include only those unvaccinated, the risk of infection is 73% higher than case rates that include both vaccinated and unvaccinated individuals.²⁸ Thus, there is an urgent need for motivational interventions to increase COVID-19 vaccine uptake in the most vaccine hesitant populations **given that they remain at risk of severe disease and death due to COVID-19.** Moreover, a successful intervention must be tailored to the needs of racial/ethnic minorities, women, rural populations and high-risk individuals with mental health and substance use disorders; groups most likely to become infected, yet least likely to accept vaccination. There is a very little research of interventions to motivate vaccine acceptance. Thus, we propose to implement and test a COVID-19 vaccination acceptance intervention that is culturally and socially acceptable, focused on the behavioral factors that increase vaccine uptake, and responsive to the needs of Veterans and VA healthcare staff.

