This is a cluster randomized parallel group trial design in which the unit of randomization will be at the level of VAMC facility. Cluster randomization is often used to avoid contamination between those receiving the intervention and those who are not. In this case, the Vaccine Acceptance Intervention will occur at Intervention sites and not at Usual Care sites, but we will monitor for evidence of contamination, and if not able to fully guard against it (VA is a national system), we will document examples of potential contamination in the environmental scans described previously.

Randomization will be stratified by VISN (either 16 or 21) and covariate constrained by baseline primary series vaccination rates.⁸¹ Given the likely relatively small number of VAMCs that will be randomized (N \leq 16), we are selecting only one stratification variable (VISN or geographic location) and one or more covariates to constrain on. We have chosen to stratify on VISN given the central importance of location on vaccination outcomes and so as not to have all VAMCs in one VISN randomly assigned to the same study arm. We will also constrain on baseline primary series vaccination rates according to whether sites have lower or higher rates at the start of the study. The number of sites that participate will guide the feasibility of constraining on additional factors, such as rurality, because current data (see **Appendix**, Table 1) suggests that rurality is an important determinant of whether individual patients accept COVID-19 vaccination.

Blinding

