8.1 Privacy and Confidentiality

8.2 Veteran Participants. Our proposed research plan involves VA-enrolled Veterans receiving care in a VISN 16 or 21 primary care clinic. We will utilize VA CDW data and other VA administrative databases to examine COVID-19 and influenza vaccine acceptance and potential predictors of Veteran vaccine acceptance including sociodemographic characteristics, mental health and medical diagnoses, and other health services utilization variables among Veterans in enrolled clinics in VISN 16 and 21. We will conduct brief surveys and qualitative interviews with a purposive sample of Veterans from enrolled sites who both received and did not receive the COVID-19 vaccine. Protected health information, as described above will be collected and stored using processes described below. Study results will be reported only in aggregate. No participant names will be used in any reports or publications.

8.2.a VA administrative data. VA CDW and other VA administrative data will be accessed through the VA Informatics and Computing Infrastructure (VINCI), an initiative to improve researchers' access to VA data and to facilitate the analysis of those data while ensuring Veterans' privacy and data security. Domains in CDW that will be accessed include Veteran sociodemographics, ICN (Integration Control Number), health services utilization, associated ICD-10 diagnoses, COVID-19 vaccine acceptance, current and prior year influenza vaccine acceptance.

8.2.b Veteran Qualitative Interviews. Qualitative interviews will be conducted by study personnel by phone. Research personnel will work in a private location. Verbal consent will be obtained over the phone and documented in study records prior to starting the interview audio-recording and the participant will not be named after that. If a participant's name is inadvertently recorded, it will be electronically stripped from the recording. Audio recordings will be retained in accordance with the VHA Records Control Schedule.

8.3Stakeholder Participants. Mid-trial and end-of-trial qualitative interviews will be conducted with VISN 16 and 21 staff with the goal of learning which aspects of the intervention and implementation were helpful, or not helpful, in improving Veteran COVID-19 vaccine acceptance. Stakeholders will be asked to consent verbally to participation. All qualitative interviews will be conducted by phone.

8.4 Data Security.

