9.1.2 Comparability of Baseline Characteristics

We will present baseline site and participant characteristics (mean, standard deviations, medians, and quartiles for continuous variables; frequency and percentages for categorical variables) by treatment group and use the summary statistics to assess for adequate balance of relevant confounders; no inferential statistics will be used. Given that the randomization was conducted at the site level and analyses will be conducted at the individual level, variables that appear to be different between the VAI and usual care arms will be adjusted for in sensitivity analyses. Study results will be reported according to the Consolidated Standards of Reporting Trials (CONSORT).

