9.1.4 Analysis of the Primary Outcome

To analyze the primary outcome (receipt of any COVID vaccination), we will use a multi-level model that considers the hierarchical clustering [Guo et al. (2000)] for a binary outcome and adjusts for region (VISN) and baseline vaccination rate to estimate the difference in proportion of vaccinated Veterans at 12-months between VAI and usual care. The model will also be *a priori* adjusted for the following participant level covariates: age, race/ethnicity, gender, health care utilization one year prior to the start of the trial. We will report the difference in rates between the VAI and usual care arms and 95% confidence interval.

Sensitivity Analyses

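### The primary model leaves out rurality and prior-year flu vaccination, two pre-baseline predictors the protocol names; the cost is a modest loss of precision and a data-dependent fallback, not bias

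*Protocol*

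**What the plan says.** **The model.** SAP 9.1.4 specifies a multi-level model that "adjusts for region (VISN) and baseline vaccination rate" and is a priori "adjusted for the following participant level covariates: age, race/ethnicity, gender, health care utilization one year prior to the start of the trial". The SAP synopsis gives the same list and places the baseline rate at facility level. SAP 9.1.5 uses identical adjustments for primary series completion.

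**The predictors.** Protocol 2.0 names as correlates of hesitancy "rurality, Republican or independent political partisanship, and not having received a flu vaccine in the prior year", alongside age, race/ethnicity and education. On rurality, the Randomization text in Protocol 5.4 adds that current study data suggest "rurality is an important determinant of whether individual patients accept COVID-19 vaccination", and Protocol 5.2.b reports that 68% of rural against 61% of urban Veterans were unvaccinated in June 2021. On flu history, Protocol 8.2.a lists "current and prior year influenza vaccine acceptance" among the Corporate Data Warehouse domains to be accessed.

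**The randomization.** Protocol 5.9 gives rural/urban distribution and facility size as examples of constraint variables for which the model adjusts. Protocol 5.4 makes constraining on rurality depend on the number of participating sites. SAP 3 reports stratification by VISN and constraint on baseline vaccination rate, nothing more.

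**The fallback.** SAP 9.1.2 says that "variables that appear to be different between the VAI and usual care arms will be adjusted for in sensitivity analyses". Balance is judged from summary statistics, without tests and without a stated threshold.

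**The concern.** Only ten sites are randomized, so differences in site make-up pass directly into the arm difference, however many Veterans are counted. Rurality and prior-year flu vaccination are fixed before site start, cannot be affected by arm, and are held by the study to matter. Left out of the primary model, any chance imbalance in them that VISN and the facility rate do not absorb stays in the primary estimate.

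The fallback does not repair this. It never changes the primary estimate, and whether it is used depends on someone's impression of the baseline table. Flu history also carries information that a facility rate cannot. The primary outcome counts any dose, boosters included, in all Veterans whatever their prior vaccination, and past flu vaccination is the one item on the protocol's list that records the individual's own vaccine behaviour.

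**Working it through.** **Step 1. Reproduce the plan's figures.** Inputs from SAP 6.1.1.1: 5 sites per arm, K = 9 or 10 clinics per site, M = 1,000 per clinic, ICCs 0.07 and 0.02, 90% power, two-sided 5%.

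- Design effect = 1 + (M − 1)(0.07) + M(K − 1)(0.02) = 1 + 69.93 + 160 = 230.93 for K = 9, and 250.93 for K = 10.
- Effective n per arm = 45,000 / 230.93 = 194.9, and 50,000 / 250.93 = 199.3.
- A pooled two-proportion calculation then gives detectable differences of 9.74/9.61 points (usual care 5%), 11.97/11.82 (10%), 13.47/13.31 (15%) and 14.55/14.37 (20%). The plan states 9.7/9.6, 12.0/11.8, 13.5/13.3 and 14.6/14.4, so all eight reproduce. Precision is set by the sites.

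**Step 2. Standard error, both arms at 20%, K = 9.** With pq = 0.16:

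Var = (2/5)[0.02(0.16) + 0.05(0.16)/9 + 0.93(0.16)/9,000] = 0.4 × 0.0041054 = 0.001642, so SE = 4.05 points.

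**Step 3. Rurality.** Gap g = 68 − 61 = 7 points (Protocol 5.2.b). The between-site SD of rural share, s, is not in the documents; I assume 10–20 points. One-SD chance shift in the arm difference = g · s · √(2/5). Variance removed by adjustment = (2/5)(g · s)².

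| s | Shift (1 SD) | Variance removed | Share of 0.001642 | SE reduction |
|---|---|---|---|---|
| 10 points | 0.07 × 0.10 × 0.632 = 0.44 points | 0.0000196 | 1.2% | 0.6% |
| 20 points | 0.07 × 0.20 × 0.632 = 0.89 points | 0.0000784 | 4.8% | 2.4% |

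These figures precede any absorption by VISN and the facility baseline rate. As an illustration, if site rural share correlated 0.5 with those terms, the shifts would shrink by √(1 − 0.25) = 0.866, to 0.38 and 0.77 points. The formula also takes the gap between individuals to equal the gap between sites.

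**Step 4. Prior-year flu vaccination.** The documents give neither a gap in COVID-19 vaccine uptake by flu history nor a between-site SD. Assuming a gap of 10–30 points and an SD of 5–10 points, the one-SD shift runs from 0.10 × 0.05 × 0.632 = 0.3 points to 0.30 × 0.10 × 0.632 = 1.9 points. Every input here is an assumption.

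**The case against.** The case for leaving the model alone is substantial.

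- **No bias.** The imbalance is chance, already part of the between-site variance that the random effects carry. The shifts above are components of the 4.05-point SE, not additions to it. This stands: a reader might infer a biased estimate or an invalid interval, and the documents support neither.
- **Partly covered.** VISN and baseline vaccination rate are controlled in the design and sit in the model, and Protocol 2.0 itself links facility rate differences to urban and rural location. This stands as a reason why the gain is smaller than computed.
- **No breach of Protocol 5.9.** A reader might infer that the SAP dropped a required adjustment. Protocol 5.9 ties adjustment to the variables used in the constraint, and SAP 3 shows rurality was not used. The two texts need reconciling, but the SAP follows that rule.
- **The pilot does not size the effect.** The single-site flu project found 39.7% versus 20.7% uptake at rural and urban clinics. A 19-point gap with s = 20 would give a 2.4-point shift and a 19% SE reduction. That reading is not supported: the outcome is 30-day flu vaccination after outreach calls in a group the protocol calls non-generalizable; rural uptake was higher, opposite to the June 2021 COVID-19 figures; and by residence the split was 32.2% versus 22.5% (p = .128).
- **Weak evidence and recording for flu history.** Protocol 2.0 says its list comes from non-VA sources. In the pilot, 290 of 488 Veterans without a documented flu vaccine (59%) reported having had one. This limits the gain, and site differences in recording could erode it further. Recording before site start cannot depend on arm, so it introduces no systematic bias.

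What does not stand is that SAP 9.1.2 is sufficient. Adjustment triggered by appearance, in a secondary position, is what prespecification avoids.

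**Conclusion.** The point holds as a worthwhile, low-cost improvement. Two predictors the protocol names are missing from the primary and secondary models, and the only route to them depends on the data.

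Rurality is the better-supported half, with a Veteran COVID-19 figure behind it: a typical chance shift of about 0.4–0.9 points against an SE of about 4.05, and an SE reduction of about 0.6–2.4% before absorption by VISN and facility rate. That rests on the assumed site SD of 10–20 points, on the plan's ICCs, and on a June 2021 unvaccinated share standing in for 12-month any-dose uptake. For flu history the size is unknown; 0.3–1.9 points is illustration only.

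**What to change.** Before unblinding, amend SAP 9.1.4 (SAP 9.1.5 follows by reference) to add two a priori Veteran-level covariates:

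1. rural versus urban residence, under one stated definition;
2. VA-recorded flu vaccination in the year before the site's initiation date.

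Keep VISN and facility baseline rate as planned. Align the example adjustment variables in Protocol 5.9 with the constraint reported in SAP 3 and the model in SAP 9.1.4.

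The cost is wording and two model terms. Prior-year flu vaccination is already a listed data domain, and the protocol already tabulates Veterans by rurality. Veteran-level terms use essentially no site-level degrees of freedom. The main limit is incomplete recording of past flu doses, which reduces the gain.

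Timing needs checking. SAP 9 permits changes up to final data lock and before unblinding, and SAP 4 assigns them to a blinded statistician, but SAP 8.1 puts the freeze at 10/19/2023 and the protocol version is dated 12.15.23. If the window has closed, run the same extended model as a fixed sensitivity analysis, reported whether or not the arms look different on these variables.
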